### **9.2 Longitudinal component:**

**Primary endpoint:** In the intervention phase, the main goal is to see whether OCA will alternate or reverse the C4(FGF19). So the main analysis to use two-sample t-test to compare the change of C4(FGF19) from baseline to 4 weeks between the randomized treated and placebo arm. The secondary analysis for the primary end points is to compare the C4 (FEF19) level at 4 week using two-sample t-tests to see whether the C4 level of the treated group has recover to the normal control level after 4 weeks treatment.

**The secondary endpoint** will be compared using two-sample t-tests in a similar way to the primary endpoints.

**Power analysis:** For the intervention study, there are 15 subjects in each group. We use two-sample t-test for comparison of the change of C4 and FGF19. With these sample size, we will have 82% power to detect any difference in change of C4(or FGF19) of effect size equal to or greater than 1.11(mean/SD) with a 5% Type I error rate.

**9.3 Safety Analysis:** Descriptive statistics will be used to summarize the AEs if occur.

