**Design**

This study consists of two groups of participants – heavy drinking adults (n=30) and non-drinking healthy controls (n=15). There are two components to this study – initial cross-sectional component followed by a 4 week longitudinal component. We are seeking to increase the overall number of subjects allowed to be consented to 150 to ensure that 30 heavy drinking adults can complete this study.

In the cross-sectional component, both groups of participants will undergo testing for bile acid metabolism, markers of gut integrity, oxidative stress, and inflammatory cytokines.

Both groups of participants will participate in the longitudinal component. While healthy controls will not receive any specific intervention, participants in the heavy drinking group will be randomized to receive either OCA (10 mg/day) or placebo for 28 days. At the end of 4 weeks, both groups of participants will again undergo testing for bile acid metabolism, markers of gut integrity, oxidative stress, and inflammatory cytokines.

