### **1.4 Rationale for Trial Design and Dose for Study Medication**

This proposed trial will evaluate the endpoints of interest between controls (n=15) and heavy drinkers (n=30). To determine the effect of OCA on FXR signaling, we will randomize heavy drinker subjects into placebo (n=15) and OCA (dose 10 mg orally once a day for 28 days, n=15).

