### **6.4 DOSE AND ADMINISTRATION**

Heavy drinker subjects will be randomized to placebo or OCA (10 mg). Study medication will be administered orally, once daily for 28 days during the study. Patients will be instructed to begin dosing on the day after the Day 0 visit and after the baseline endpoint measurements are obtained (i.e., on Day 1) and to take study medication with water, approximately 30 minutes prior to breakfast. Patients must be instructed to swallow the tablet whole; they must not chew, divide, or crush the tablet.

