#### **Day 0 Procedures (Randomization and Baseline Study Day)**

- Review inclusion and exclusion criteria for eligibility
- Record vital signs
- Perform a Physical Examination
- Assess and record any pretreatment emergent events
- Record prior (within 30 days of Day 0) and current concomitant medications
- Assess Alcohol Consumption
- Perform an urine pregnancy test in females of childbearing potential
- Perform Hepatic CYP2E1 Measurement Study
- Perform Gut Permeability Test (Lactulose/ Mannitol test)
- Obtain safety labs (CMP, CBC and PT/INR)
- Obtain Research Blood samples as outlined in Table 1: Schedule of Study Procedures
- Obtain Stool Specimen (optional)
- Randomization to study drug (*Heavy drinker group only*)
- Dispense study drug (*Heavy drinker group only*) and instruct patient to begin dosing on the day after Day 0 visit and to take the study medication with water approximately 30 minutes prior to breakfast.

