## **9. STATISTICAL METHODS**

### **9.1 Cross-sectional Component:**

**Primary end point:** The mean(SD) will be used to summarize the baseline the C4 and FGF19 level at baseline. The primary analysis is to compare the C4 and FGF19 level at baseline between the 15 health control and 30 heavy drinker using independent two-sample t-tests. The distribution assumption of C4 and FGF19 will be examined for the distribution assumption. If there is an assumption violation, appropriate transformation will be used to correct the assumption violation. We will also perform analysis of covariance (ANCOVA) analysis with C4(FGF19) at baseline as the outcome variable, group(health control vs. heavy drinker) as the main predictor adjusting for patients' characteristics.

**The secondary endpoints** (a) fasting serum bile salt levels, oxidative stress and CYP2E1 activity; (c) gut permeability, bacterial translocation, and intestinal inflammation; and (d) activation of innate immunity at baseline will also be compared using two-sample t-test and the ANCOVA models in a similar way to C4 and FGF19.

**Power analysis:** For the cross-sectional study, there are 15 health and 30 heavy drinker. We use two-sample t-test for comparison of the primary endpoint C4 and FGF19. With these sample size, we will have 83% power to detect any difference in C4(or FGF19) of effect size equal to or greater than 0.95(mean/SD) with a 5% Type I error rate.

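### The only randomised comparison (15 v 15) is analysed by an unadjusted t-test on change; the test is valid, but ANCOVA on the Day 0 value would usually be more efficient

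*Combined protocol and SAP*

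**What the plan says.** Only the heavy drinkers are randomised. Section 1.4 states "we will randomize heavy drinker subjects into placebo (n=15) and OCA" (also 15), and the power paragraph of Section 9.2 repeats the number: "For the intervention study, there are 15 subjects in each group". The main longitudinal analysis in Section 9.2 is a "two-sample t-test to compare the change of C4(FGF19) from baseline to 4 weeks between the randomized treated and placebo arm". The week-4 level is also compared by t-test, and the longitudinal secondary endpoints "will be compared using two-sample t-tests in a similar way to the primary endpoints".

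The only ANCOVA is in Section 9.1. There the baseline level is the outcome and the contrast is healthy controls against heavy drinkers, so it does not address OCA against placebo.

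The covariate is already collected. The Day 0 procedures in Section 7.2 include "Obtain Research Blood samples as outlined in Table 1: Schedule of Study Procedures", and the footnote to that table lists C4 and FGF19. Section 6.4 tells patients to "begin dosing on the day after the Day 0 visit and after the baseline endpoint measurements are obtained", so the Day 0 value precedes treatment.

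For the cross-sectional analysis, Section 9.1 adds: "If there is an assumption violation, appropriate transformation will be used to correct the assumption violation". Section 9.2 has no equivalent sentence.

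**The concern.** A change score uses the Day 0 value but assumes that each unit of difference at Day 0 carries through in full to week 4 (slope 1). The true within-arm slope is ρ × (SD at week 4 / SD at Day 0). When it is well below 1, subtracting the whole baseline adds noise that ANCOVA would remove.

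The same loss can be seen conditionally. If the arms differ by chance by b at Day 0, the change-score estimate moves by (1 − slope) × b in the opposite direction. With 15 per arm, the standard error of b is √(2/15) = 0.365 Day 0 SDs. At a slope of 0.5, an imbalance of one standard error therefore shifts the estimate by 0.5 × 0.365 = 0.18 Day 0 SDs. Over repeated randomisations this averages to zero, so it is imprecision and not a separate bias.

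At stake is the precision of the only randomised evidence on OCA. That evidence comes from 30 people, and the plan is powered only for a large effect (1.11 SD of change).

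**Working it through.** **Inputs from Section 9.2:** n = 15 per arm; effect 1.11 SD of change; type I error 5% (sidedness not stated, taken as two-sided); stated power 82%.

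**Inputs assumed:** the Day 0 to week-4 correlation ρ; the ratio r = SD(week 4)/SD(Day 0); and a covariance structure common to both arms. The documents give none of these, so a range is shown.

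**Step 1: the plan's own figure.** The noncentrality is 1.11/√(2/15) = 3.040 on 28 df, with critical value 2.048. Noncentral t power is 83.5%, against 82% stated, so the figure reproduces. The effect detectable at exactly 82% power is 1.09 SD of change.

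**Step 2: ANCOVA variance relative to the change score.** With the Day 0 SD set to 1, the change score has variance 1 + r² − 2ρr, and the ANCOVA residual has variance r²(1 − ρ²). Estimating the slope inflates the variance by a factor of 1 + 1/(30 − 4) = 1.038 on average. Residual df fall from 28 to 27 (critical value 2.052). For equal SDs (r = 1) the ratio simplifies to (1 + ρ)/2 × 1.038.

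Example, ρ = 0.5 and r = 1: the ratio is 0.75 × 1.038 = 0.779; the noncentrality is 3.040/√0.779 = 3.44; power is 91.3%.

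**Step 3: equal SDs.** The t-test has 83.5% power throughout.

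| ρ | Variance ratio | ANCOVA power | Detectable effect at 82% power (SD of change) | t-test n per arm with the same power |
|---|---|---|---|---|
| 0.3 | 0.67 | 94.6% | 0.895 | 21.6 |
| 0.5 | 0.78 | 91.3% | 0.96 | 18.9 |
| 0.7 | 0.88 | 87.7% | 1.02 | 16.8 |
| 0.8 | 0.93 | 85.8% | 1.05 | 15.9 |
| 0.9 | 0.99 | 83.9% | 1.08 | 15.2 |
| 0.95 | 1.01 | 83.0% | 1.10 | 14.8 |

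The variances are equal at ρ = 2/1.038 − 1, about 0.93.

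**Step 4: unequal SDs.** ANCOVA power at ρ = 0.3, 0.5, 0.7, 0.8 and 0.9:

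- r = 1.25: 90.1%, 86.1%, 82.7%, 82.0%, 83.9%
- r = 1.5: 86.9%, 83.4%, 82.1%, 83.8%, 90.3%
- r = 0.75: 97% to 99% throughout

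**Step 5: worst case.** When ρr = 1, the change-score variance (r² − 1) equals the ANCOVA residual variance (r² − 1), so only the cost of estimating the slope remains. Examples are ρ = 0.5 with r = 2, and ρ = 0.7 with r = 1.43. The noncentrality is 3.040/√1.038 = 2.98 and power is 82.0%, a loss of 83.5 − 82.0 = 1.5 points.

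**Step 6: validity.** In simulations with no treatment effect, both tests rejected in about 5% of runs (4.8% to 5.3%). Simulated power agreed with the formulas to within about half a point.

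**The case against.** The strongest reply is that nothing here is wrong. The test, effect size, sample size and stated power in Section 9.2 agree with one another, and the test holds its level. That stands: this is a choice between two valid analyses.

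The size of the gain cannot be fixed from the documents. The 11-point figure (94.6 − 83.5) belongs to the lowest correlation shown, with equal SDs. Section 1.4 reports that FGF19 rose with OCA dose. If its spread rises with its level, r could exceed 1 on the raw scale and the gain could be small or slightly negative (Step 4). C4 could go the other way, because OCA lowers it. This stands too, but the trade is lopsided: at 15 per arm the loss does not exceed about 1.5 points, while the gain can be several times that. Not knowing the slope is a reason to estimate it.

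Section 9.2 asks about change. With Day 0 in the model, however, ANCOVA of change and ANCOVA of the week-4 value give the same treatment effect, so the question is unaltered.

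The Synopsis raises the consent ceiling to 150 "to ensure that 30 heavy drinking adults can complete this study". That secures the planned number of completers. ANCOVA would not reduce it, so the equivalent sample sizes in Step 3 measure precision and are not a saving in recruitment.

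Two smaller points also stand. The missing distribution check in Section 9.2 is separate from the choice of test. And stool collection is optional, so calprotectin may have fewer pairs: if only 8 per arm had both samples (an assumption), the worst-case loss would be 54.3% to 50.9%, about 3.4 points.

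**Conclusion.** The concern holds as a recommendation on efficiency. The planned change-score t-test is valid and its stated power is right, but it leaves unused some of the precision available from a baseline value the trial already measures.

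With equal SDs, the gain at the plan's effect size runs from about 11 points of power at ρ = 0.3, through about 8 at 0.5 and 4 at 0.7, to under 1 at 0.9; by 0.95 there is a loss of about half a point. Across all the SD ratios examined, the largest loss at 15 per arm is about 1.5 points, when the true slope is 1.

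These figures rest on assumed correlations and SD ratios, a common covariance in both arms, a two-sided 5% test and 15 completers per arm. The direction usually favours ANCOVA; the amount is unknown until the data are seen.

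**What to change.** Amend Section 9.2 before any comparison of the arms is run:

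1. Make the primary analysis of C4, and likewise of FGF19, an ANCOVA of the week-4 value on randomised arm and Day 0 value.
2. State that the distribution check and transformation of Section 9.1 also apply here, with the same scale used at both visits.
3. Keep the two-sample t-test on change as a sensitivity analysis.
4. Use the same model for OCA against placebo on the longitudinal secondary endpoints, noting that the cost of estimating the slope is larger where few pairs are available, as may happen with stool calprotectin.

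The cost is SAP wording, one residual degree of freedom (28 to 27) and an average variance inflation of about 4% for estimating the slope; both are already in the power figures above. No extra visits, samples or participants are needed.

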### **Day 28 Procedures (+/- 2 days)**

Healthy non-drinkers controls will have repeated procedures at D0 performed. The same procedures will also be done in heavy drinkers when they complete the study drug for 28-day.

- Record vital signs
- Perform a Physical Examination
- Assess and record any Adverse Events
- Assess concomitant medications
- Perform a standard 12 Lead Electrocardiogram (*Heavy Drinker Group only*)
- Obtain Safety Labs (CBC, CMP and PT/ INR) (*Heavy Drinker group only*)
- Evaluation of Study Drug Compliance (*Heavy Drinker Group only*)
- Collection of all study medication and bottles (*Heavy Drinker Group only*)
- Assess Alcohol Consumption
- Perform Hepatic CYP2E1 Measurement Study
- Perform Gut Permeability Test (Lactulose/ Mannitol test)
- Obtain Research Blood samples as outlined in Table 1: Schedule of Study Procedures
- Obtain Stool Specimen (optional)
- Perform an urine pregnancy test in females of childbearing potential

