#### **HANDLING OF MISSING DATA**

Missing values will not be imputed and only observed values will be used in data analyses and presentations.

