### **10.2 INSTITUTIONAL REVIEW BOARD (IRB)**

A properly convened IRB at each participating site will review and approve this study prior to its initiation. All protocol amendments will be reviewed and approved by the IRBs. Amendments can be implemented only following the IRB approval unless the amendment is necessary to reduce immediate risk to trial participants.

The IRB will be informed of any new safety information that negatively affects the risk assessment of the trial as soon as it becomes available.

Investigators or the Sponsor or its designee will provide reports to the IRB/IEC as requested, as a minimum annually, and after the trial is complete.

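### The week-4 analysis in 9.2 asks whether treated drinkers have returned to the control level, but a non-significant t-test at 15 v 15 does not show that they have

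*Combined protocol and SAP*

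**What the plan says.** Section 9.2 makes the change in C4 and FGF19 from baseline to 4 weeks, OCA against placebo, the main longitudinal analysis. The secondary analysis of the same endpoints is to "compare the C4 (FEF19) level at 4 week using two-sample t-tests" (FEF19 is presumably FGF19), with the aim "to see whether the C4 level of the treated group has recover to the normal control level after 4 weeks treatment". The sentence does not say which groups are compared. Because the aim refers to the control level, OCA arm against healthy controls is the natural reading.

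The data for that comparison will exist. The Synopsis (Design) says "At the end of 4 weeks, both groups of participants will again undergo testing for bile acid metabolism", and the Day 28 procedures in 7.2 say "Healthy non-drinkers controls will have repeated procedures at D0 performed".

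The two power statements cover other comparisons: baseline drinkers against controls in 9.1, and change in OCA against placebo in 9.2. Nothing in the document defines recovery, sets a margin, or gives a confidence-interval rule or power for the week-4 comparison with controls. The next sentence of 9.2 extends the approach to the secondary endpoints.

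**The concern.** The question is one of similarity: are treated drinkers now like controls? The tool is a test of difference, and its two outcomes do not match the two possible answers. A significant result says the levels differ, and its sign says whether the OCA arm falls short of the controls or has gone past them. A non-significant result says only that 15 per group did not reveal a difference, which is expected under full recovery and also quite likely under incomplete recovery.

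Reversal by OCA of the alcohol-related abnormality is a stated hypothesis (1.1 and section 2). The randomised comparison shows whether OCA moves C4 and FGF19 relative to placebo. Only this secondary sentence asks whether they return to the control level. At stake is whether a statement that OCA normalises C4 or FGF19 could rest on a p-value above 0.05. The same applies to any secondary endpoint compared with controls at week 4 in the same manner.

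**Working it through.** **Inputs.** 15 on OCA (1.4 and 9.2), 15 healthy controls (9.1), 5% type I error (9.1 and 9.2). Sidedness is not stated; I take two-sided. Differences are in units of a common SD. The document gives no expected drinker-control gap, so remaining differences are shown over a range.

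**Plan's own figures first.** Noncentral t, two-sided 5%, with df = n1 + n2 − 2 and noncentrality = d / √(1/n1 + 1/n2):

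- 15 v 15, d = 1.11: power 83.5% (plan: 82%)
- 15 v 30, d = 0.95: power 83.6% (plan: 83%)

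Both agree within 2 points, so the two-sided reading is reasonable and the plan's arithmetic is not at issue.

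**Chance of a non-significant week-4 result, 15 v 15.** SE = √(2/15) = 0.365 SD, df = 28, critical t = 2.048.

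| True difference remaining (SD) | Noncentrality | P(non-significant) |
|---|---|---|
| 0 | 0 | 95% |
| 0.5 | 0.5/0.365 = 1.37 | 74% |
| 0.75 | 0.75/0.365 = 2.05 | 49% |
| 0.95 | 0.95/0.365 = 2.60 | 29% |
| 1.11 | 1.11/0.365 = 3.04 | 16.5% |

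The 0.95 row is the plan's own detectable effect in 9.1 ("effect size equal to or greater than 0.95(mean/SD"). If the gap were 0.95 SD and OCA closed none of it, nearly three trials in ten would still give a non-significant week-4 test.

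**Precision.** Expected 95% CI half-width is about 2.048 × 0.365 = 0.75 SD. An observed difference smaller than this is non-significant.

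**What a real equivalence claim would need.** One-sided 5% tests, true difference zero, 15 v 15:

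| Margin | Two-sided margin (two one-sided tests) | One-sided margin |
|---|---|---|
| 0.475 SD | 0.3% power | 35% power |
| 0.95 SD | 63% power | 81% power |
| Margin giving 80% power | about 1.10 SD | about 0.93 SD |

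The document gives no margin; 0.475 and 0.95 SD are half and all of the effect that 9.1 can detect. An 80%-power margin is therefore about as wide as that effect, or wider.

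**The case against.** **A yes is possible.** A reader might infer that this test can never support recovery. That goes too far. Section 1.1 gives directions (C4 raised and FGF19 lowered in drinkers), and the dose rationale in 1.4 reports that OCA lowers C4. If recovery means reaching the control level or going beyond it, a significant result with treated C4 below control would support it. This stands, but it helps little. Take a 0.95 SD gap and a change effect of 1.11 SD of change. At an assumed within-person correlation r of 0.3 to 0.7, that effect is 1.11 × √(2(1 − r)) = 1.31 to 0.86 SD of level. The remaining difference is 0.95 − 1.31 = −0.36 to 0.95 − 0.86 = +0.09 SD. An overshoot of 0.36 SD would be significant in only about 16% of trials at 15 v 15. The plan's wording can also be read as return to the level, not beyond it.

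**The plan never equates p > 0.05 with recovery.** Correct, and it should not be accused of doing so. The fault is that the stated test does not fit the stated aim and nothing guards against that reading.

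**Partial recovery is hypothetical.** Also fair. On the plan's two effect sizes, little or none of a 0.95 SD gap would remain. But those are detectable effects, not expected ones, so they do not rule partial recovery out. The table above is conditional on the remaining difference and does not predict one. The CI width and margin figures do not depend on the gap.

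**Numbers may fall below 15 v 15.** A reader might infer worse precision from the rule "Missing values will not be imputed and only observed values will be used in data analyses and presentations". The document gives no dropout rate, and the Synopsis raises the consent ceiling to 150 so that 30 drinkers finish. I therefore keep 15 v 15; missing Day 28 assays or control dropout would widen the interval.

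**The groups may be otherwise.** The sentence might also include OCA against placebo at week 4. That comparison alone cannot address the control level, so the groups need naming in either case.

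**Conclusion.** The point holds in limited form. A non-significant week-4 t-test at 15 v 15 does not establish return to the control level: it occurs about 29% of the time with 0.95 SD remaining and about 74% with 0.5 SD remaining. These figures assume two-sided 5%, a common SD, approximate normality on the analysis scale and complete data. The plan supplies no margin, CI criterion or power that would turn the comparison into a test of recovery, and it leaves the groups unnamed.

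It does not follow that the trial's main conclusion is at risk. The randomised comparison of change is separate and unaffected. Nor is adding a formal equivalence test the obvious remedy, since the margin it could support at this size is about 0.93 SD (one-sided) to 1.10 SD (two-sided). Even when well estimated, OCA arm against controls is a non-randomised comparison. Severity is minor to moderate, in a secondary analysis only.

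**What to change.** Replace the secondary-analysis sentence in 9.2 with wording such as:

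> As a descriptive, non-randomised secondary analysis, Day 28 C4 and FGF19 will be compared between the OCA arm and the healthy controls. The difference (OCA minus control), its direction and its 95% CI will be reported on the scale used in 9.1. A non-significant difference will not be reported as recovery. Any claim of recovery or equivalence requires a margin, stated as one- or two-sided, justified and fixed before the data are seen. The same rule applies to any secondary endpoint compared with controls at week 4.

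The scale matters because 9.1 provides that, if assumptions fail, "appropriate transformation will be used to correct the assumption violation"; the week-4 estimate should follow the same choice. If a week-4 OCA-v-placebo comparison was also intended, keep it as a separate, named item so that the rewrite does not delete it. State the expected half-width of about 0.75 SD at 15 v 15 so readers know what the interval can and cannot exclude. An adjusted estimate is optional. If used, it should be limited to a few covariates named in advance, since 9.1 names none.

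Cost: a wording amendment, which needs ethics review (10.2: "All protocol amendments will be reviewed and approved by the IRBs"). No new visits, samples or participants are required. The price is that a non-significant p-value can no longer be presented as normalisation.

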### Treatment phase,

This investigation will consist of the following 2 study groups:

**Group A:** Healthy non-drinker controls (n = 15)

**Group B:** Heavy drinkers with no known history of liver disease (n=30)

Heavy alcohol drinking will be defined as ongoing consumption > 40 grams per day or >98 grams in a week on average in women and > 60 grams per day or >196 grams in a week on average in men for a minimum of the past 6 months and within the 3 months prior to study enrolment. Judgment regarding daily and yearly alcohol use will be made by the site investigator. During recruiting we will inform the patient that this level of drinking is harmful and will offer referral for treatment. Absence of liver disease will be ascertained according to predefined criteria. Alcohol consumption will be quantified by interview and by a standard alcohol consumption questionnaire.

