**Plasma bile salts are elevated in most patients with alcoholic hepatitis (with or without clinical cholestasis)**. Intrahepatic cholestasis correlates with elevated bile salt levels, Maddrey Discriminant Function, histological severity, and survival. Many patients without histological cholestasis had elevated bile salt levels. There is little information about the effect of heavy alcohol use on bile salt metabolism. Vendemiale and Lieber reported that rats chronically fed a high alcohol diet had increased secretion of bile salts into the bile. Ackehed et al., measured fecal bile salts in 7 patients at admission for detoxification and 9 days later. They found that bile salt excretion was over twice that of normal controls, and slowly declined during abstention. Since the rate of bile salt excretion in steady state must equal bile salt synthesis, this might reflect increased rates of synthesis of bile salts in heavy drinkers, consistent with our hypothesis regarding effects of alcohol on CYP7A1 expression. This elevation in bile salts ought to activate the FXR signaling pathway, with a return of bile salt levels toward normal: the fact that bile salt levels are nearly always increased in AH suggests that this homeostatic system is impaired. As shown in Figure 1, alcohol feeding of mice for 4 weeks reduces levels of Shp. We do not know how alcohol feeding reduced Shp levels. We have previously shown that RXRa protein levels were reduced by alcohol feeding [18]; additional possibilities include direct effects on FXR and reduction in *cis*-retinoic acid, the ligand for RXR^28. We suggest that a primary effect of heavy alcohol use in patients with alcoholic liver disease is inhibition of the ability of FXR to induce Shp. This would result in increased levels of CYP7A1 and sinusoidal bile salt uptake pump, and reduction in the bile salt export pump, resulting in elevated plasma and hepatocyte bile salt levels.

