## 5. PATIENT SELECTION

### 5.1 PATIENT POPULATION

Prospective patients will be identified primarily from the hospitals including Fairbanks Drug and Alcohol Rehabilitation Hospital, outpatient clinics, self-referrals or may be referred by physicians from other hospitals and clinics. Throughout this protocol, the terms 'Principal Investigator (PI)', 'investigator' and 'investigator or designee' are used synonymously. Irrespective of the term used, the intention remains the same: that the overall trial responsibility remains with the PI who has agreed to personally conduct or supervise the trial and who may delegate aspects of the trial conduct, to appropriate, qualified trial site staff who have been informed about their obligations in meeting the above commitments.

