#### **Day 7 Procedures (+/- 2 days)- *Heavy Drinker Group Only***

- This consists of a telephone visit where the study staff will inquire with the subject on his/her wellbeing, compliance with study medication, adverse events and concomitant medication use.

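### The secondary week-4 recovery analysis in section 9.2 names only the OCA arm against healthy controls, so recovery from reduced drinking could be read as reversal by OCA

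*Combined protocol and SAP*

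**What the plan says.** Section 9.2 sets two analyses of the primary endpoints. The main one is a two-sample t-test to "compare the change of C4(FGF19) from baseline to 4 weeks between the randomized treated and placebo arm". The secondary one compares week-4 levels, again by two-sample t-tests, "to see whether the C4 level of the treated group has recover to the normal control level after 4 weeks treatment". No margin defines recovery, and no comparison of placebo with controls is named.

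Three other places bear on how drinking may change after Day 0:

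- Synopsis, Treatment phase: "During recruiting we will inform the patient that this level of drinking is harmful and will offer referral for treatment".
- Section 5.1: patients are "identified primarily from the hospitals including Fairbanks Drug and Alcohol Rehabilitation Hospital", as well as from clinics, self-referral and physician referral.
- Section 1.1, on a small study of patients admitted for detoxification: "They found that bile salt excretion was over twice that of normal controls, and slowly declined during abstention".

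Alcohol history is taken at Screening, Day 0 and Day 28 (Table 1). The Day 28 list in section 7.2 includes "Assess Alcohol Consumption". Section 9.2 does not use these data as a summary, covariate or sensitivity analysis.

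**The concern.** Section 2 asks whether the effect of alcohol on FXR can be reversed by OCA. The week-4 comparison with healthy controls appears to answer that most directly, but it is not randomised: it sets treated drinkers against people who never had the exposure. If participants cut down during the 28 days, for which the trial itself gives them reason, C4 and FGF19 may move towards control values without any drug effect. The placebo arm is the only group that shows how much of this happens unaided, and this comparison does not name it.

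A second weakness compounds the first. With no margin and 15 per group, the natural way to read the t-test is that a non-significant difference means recovery. At this size a non-significant result is weak evidence of that.

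**Working it through.** **Inputs.** From section 9: 15 OCA, 15 placebo, 15 controls; effect sizes of 0.95 SD (cross-sectional) and 1.11 SD (change); 5% type I error, taken as two-sided because sidedness is not stated. Assumptions: the true drinker-control gap in SD units, and the share f of it that closes through reduced drinking. The documents give neither, so ranges are shown.

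**Step 1: the plan's own power.** Noncentrality = d / √(1/n₁ + 1/n₂), referred to the noncentral t.

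- Longitudinal: 1.11 / √(2/15) = 1.11 / 0.365 = 3.04 on 28 df; power 0.835, against the stated 82%.
- Cross-sectional: 0.95 / √(1/15 + 1/30) = 0.95 / 0.316 = 3.00 on 43 df; power 0.836, against the stated 83%.

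Both reproduce to within 2 percentage points.

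**Step 2: the recovery analysis when OCA does nothing.** The residual gap at week 4 is g = gap × (1 − f), and the noncentrality is g / 0.365 on 28 df. The table gives the probability that OCA v control is not significant.

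| Share of gap closed | Residual, gap 0.95 SD | P(not significant) | Residual, gap 1.11 SD | P(not significant) |
|---|---|---|---|---|
| 0% | 0.95 | 0.29 | 1.11 | 0.165 |
| 25% | 0.71 | 0.53 | 0.83 | 0.405 |
| 50% | 0.475 | 0.76 | 0.555 | 0.69 |
| 75% | 0.24 | 0.90 | 0.28 | 0.89 |
| 100% | 0 | 0.95 | 0 | 0.95 |

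The first row is due to sample size alone. The rise below it is due to drinking.

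**Step 3: precision.** The 95% CI half-width at 15 v 15 is 2.048 × 0.365 = 0.75 SD. Even an observed difference of zero would leave a residual gap of up to 0.75 / 0.95 = 79% of the assumed gap within the interval.

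**Step 4: what placebo would show, and the main test.** A simulation (20,000 runs; SD 1 at each visit; baseline-to-week-4 correlation 0.5, assumed; no OCA effect; the same share of each arm stopping and losing the whole 0.95 SD gap) gave:

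| Share stopping, both arms | OCA v control not significant | Placebo v control not significant | Randomised change test significant |
|---|---|---|---|
| 0% | 0.293 | 0.293 | 0.049 |
| 25% | 0.558 | 0.553 | 0.049 |
| 50% | 0.779 | 0.780 | 0.050 |
| 75% | 0.911 | 0.909 | 0.049 |
| 100% | 0.953 | 0.951 | 0.050 |

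Placebo appears to recover as often as OCA, so showing it alongside would expose the problem. The randomised test holds its 5% level throughout.

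**The case against.** The strongest reply is that reversal is judged first by the main analysis, which is randomised and placebo-controlled. That stands. A fall in drinking common to both arms cancels there, and the exposed analysis is labelled secondary.

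A reader might infer that, with 15 per arm, a chance imbalance in who stops drinking could drive the main result. That does not follow, because the t-test's standard error already allows for such imbalance. With 20% or 40% stopping in each arm and an assumed 1 SD shift, the simulated false-positive rate is about 5%. An imbalance of three stoppers would move the arm difference by 3/15 × 1 SD = 0.20 SD, against a standard error of 0.365 SD. A reader might also infer a serious loss of power. The documents give no stopping rate, no size of shift and no sign that OCA works less well in those who stop, so they support no such figure.

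The evidence in section 1.1 is indirect. It concerns faecal bile salts in 7 patients measured at admission and 9 days later; it describes the decline as slow, and the protocol says only that excretion might reflect synthesis. It gives a reason to guard against natural recovery, but does not show that C4 or FGF19 will normalise within 28 days.

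Finally, section 9.2 speaks of t-tests in the plural, which may have been meant to include placebo. Only the treated group is named, and one sentence would settle it.

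**Conclusion.** The point holds for the secondary recovery analysis only. As written, that analysis cannot separate an OCA effect from the effect of drinking less, and reading non-significance as recovery makes this worse. With no OCA effect and an assumed 0.95 SD gap, the OCA arm would look recovered in 29% of trials with no natural recovery and in 76% if half the gap closes; with a 1.11 SD gap the figures are 16.5% and 69%. The gap and the share closed are assumptions. The documents say why drinking may fall, but not by how much.

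It would be wrong to conclude that the trial's main answer on reversal is confounded by abstinence: the randomised comparison of change is valid as planned. Nor are data lacking, since drinking is recorded at Day 0 and Day 28. This is a gap in the analysis plan that should be closed, and closing it costs almost nothing.

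**What to change.** In section 9.2:

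1. Run the same week-4 comparison with controls for the placebo arm, presented beside the OCA arm.
2. Report both as differences with 95% confidence intervals, and state that a non-significant difference is not taken as recovery.
3. State that only recovery beyond placebo, as shown by the randomised comparison, is attributed to OCA.
4. Tabulate change in alcohol intake from Day 0 to Day 28 by arm.
5. If an OCA v placebo estimate among continuing drinkers is wanted, specify it in advance as supportive and non-randomised. It selects on behaviour after randomisation and on reported intake, and it is small: if 40% stopped, 15 × 0.6 = 9 per arm would remain, with about 60% power at 1.11 SD.

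The unadjusted randomised comparison stays as the main analysis, and counselling and referral are untouched. The cost is a few sentences of analysis text and one table. Controls and both drinker arms already give research blood at Day 28, so no new visit, sample or question is needed.
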